3.4 Immunogenicity Analysis Set

Immunogenicity analysis set includes all participants from Cohorts 1 and 2 in the safety analysis set who also have baseline and at least one post-baseline evaluable data point. Data will be analyzed by treatment group based on actual treatment received.

3.5 Pharmacodynamic Analysis Set

Pharmacodynamic (PD) analysis set includes all participants from Cohorts 1 and 2 in the safety analysis set who also have baseline and at least one post-baseline evaluable PD/biomarker data point. Data will be analyzed by treatment group based on the actual treatment received.

4. ANALYSIS VARIABLES

4.1 Demographic and Baseline Characteristics

The following demographic and Baseline characteristics variables will be summarized:

- Demographic variables: Age, Sex, Ethnicity, Race, Height, Baseline weight, Baseline body mass index (BMI).
- Baseline AD Characteristics: Duration of AD, Atopic comorbidities, EASI, IGA (Moderate or Severe), AD involvement of body surface area (BSA), SCORAD, itch NRS, sleep quality NRS, PGIS, DLQI, and thymus and activation-regulated chemokine (TARC).

Duration of AD will be calculated as:

$$(\text{Date of enrolment} - \text{Diagnosis date of AD})/365.25.$$

In cases where only a partial date is available for AD diagnosis, the imputation process will involve substituting "01" if only the day is absent, or "01 Jan" if both the day and month are missing, prior to the calculation of the duration.

4.2 Medical History and Atopic Disease History

Medical history will be coded according to the latest available version (26.0 or higher) of medical dictionary for regulatory activities (MedDRA) at the coding contract research organization (CRO). Information on conditions related to AD includes diagnosis of AD, AD history, applicable atopic/allergic diseases etc.

4.3 Prior and Concomitant Medications/Procedures

Medications/Procedures will be recorded from the day of informed consent until the EOS visit. Medications will be coded according to the latest available version (WHO Drug B3 Global, Sep 2022 or higher) of World Health Organization Drug Dictionary (WHODrug) at the coding CRO.

Prior medications/procedures: Medications taken or procedures performed prior to the first dose of Investigational Medicinal Product (IMP). All the medications that are stopped prior to the first administration of the study drug are considered under this category.

Concomitant medications/procedures: medications taken or procedures performed following the first dose of study drug through the EOS visit. i.e., procedures or medication with end date on or after the first administration of the study drug irrespective of the start date, or ongoing during the study period.

Prohibited medications and non-drug therapies:

Treatment with the following concomitant medication is prohibited from screening to study completion:

- Topical treatment including, but not limited to, TCS, TCI, topical phosphodiesterase-4 inhibitors, and topical janus kinase (JAK) inhibitors for AD within 2 weeks before the Baseline visit and until completion of the follow-up period. Current use of nasal or inhaled corticosteroids is allowed during the study.
- Non-biologic systemic (oral or injectable) agents including conventional immunosuppressants or immunomodulators (e.g., corticosteroids, methotrexate, cyclosporin, tacrolimus, mycophenolate mofetil, azathioprine, JAK inhibitors), and other approved drugs with potential immunosuppressive effects, within 4 weeks or 5 half-lives, whichever is longer, prior to the Baseline (Day 1) visit and until completion of the follow-up period.
- Biologic therapy including approved and investigational agents (e.g., mAbs against IL-13 or IL-4 alpha, investigational mAbs against IL-31 or IL-31 receptor) within 3 months or 5 half-lives, whichever is longer, prior to the Baseline (Day 1) visit and until the completion of the follow-up period.
- Treatment with a live (including live attenuated) vaccine within 2 months before the Baseline visit and until 3 months after the last administration.

The following concomitant procedures are prohibited during study participation:

- Phototherapy of AD with UVA or UVB or regular use of a tanning booth within 4 weeks of the Baseline visit and until the completion of the follow-up period.

Rescue therapy: If medically necessary (i.e., to control intolerable AD symptoms), rescue treatment for AD may be prescribed to study participants at the discretion of the investigator. Any participant who requires topical corticosteroid (TCS) treatment may continue study treatment and should receive the TCS for as brief a period as possible. TCIs may be used for rescue, but should be reserved for problem areas only, e.g., face, neck, intertriginous and genital areas, etc. If a participant receives rescue treatment with a prohibited systemic medication, study treatment should be permanently discontinued.

If possible, investigators should attempt to limit the first step of rescue therapy to topical medications and escalate to systemic medications only for participants who do not respond adequately to at least 7 days of topical treatment. Where feasible, an unscheduled visit should

be performed to conduct all efficacy and safety assessments (as well as PK/PD sampling, if it is feasible) before administering any systemic rescue treatment.

4.4 Prior and concomitant non-drug therapies and procedures

Non-drug therapies will be recorded from the day of informed consent until the EOS visit and each therapy will be coded according to the latest available version (26.0 or higher) of MedDRA.

4.5 Efficacy Variables

Since the primary objective of the study is to assess the safety arising from multiple doses of IMG-007, the analysis of efficacy will be conducted as secondary and exploratory.

4.5.1 Secondary Efficacy Variable

The secondary efficacy endpoint is the percentage change in EASI from baseline to week 12.

Eczema Area and Severity Index (EASI)

The EASI is a validated composite scoring system assessed by the investigator based on the body area involved in each of the four body regions (head and neck, upper limbs, lower limbs, and trunk) and the average severity of each of the four key signs of AD (erythema, edema/papulation, excoriation, and lichenification) based on a 4-point scale of 0 (none), 1 (mild), 2 (moderate), and 3 (severe), ([Hanifin 2001](#)). Symptoms (e.g., pruritus) and secondary signs (e.g., xerosis, scaling) are excluded from the assessment. The total EASI score ranges from 0 (clear or no eczema) to 72 (maximum severity), with the higher values indicating more severe and/or extensive disease. A score of 0 to 72 will be recorded. All assessments will be recorded in an appropriate electronic case report form (eCRF) according to the completion guidelines.

The EASI will be assessed by the investigator at selected scheduled and unscheduled clinic visits.

The EASI score will be computed at the dataset level, irrespective of its presence in the eCRF. However, the EASI score recorded in the eCRF will be utilized for the efficacy analysis. The derivation of EASI score is provided in the [Appendix 12.3](#).

4.5.2 Exploratory Efficacy Variables

4.5.2.1 Key Exploratory Endpoints

The key exploratory endpoints are:

- Mean and mean % change from baseline in EASI by visit
- Proportion (%) of participants achieving EASI-50 by visit
- Proportion (%) of participants achieving EASI-75 by visit
- Proportion (%) of participants achieving EASI-90 by visit
- Mean change from baseline in IGA by visit
- Proportion (%) of participants achieving \geq 1-point reduction from baseline in IGA by visit

- Proportion (%) of participants achieving \geq 2-point reduction from baseline in IGA by visit
- Proportion (%) of participants achieving IGA 0 or 1 (clear or almost clear) and \geq 2-point reduction from baseline by visit
- Mean and mean % change from baseline in SCORAD and Objective-SCORAD (O-SCORAD) by visit
- Mean and mean % change from baseline in worst itch numerical rating scale (WI-NRS) by visit
- Proportion (%) of participants achieving a \geq 4-point reduction from baseline in WI-NRS by visit in participants with WI-NRS \geq 4 at Baseline
- Mean and mean % change from baseline in sleep quality numerical rating scale (SQ-NRS) by visit

Investigator's Global Assessment (IGA)

The IGA is intended to assess the global severities of key acute clinical signs of AD, including erythema, induration/papulation, oozing/crusting (lichenification excluded) based on a 5-point scale of clear (0), almost clear (1), mild (2), moderate (3) and severe (4). A grade of 0 to 4 will be scored by the investigator. Assessments will be recorded in the eCRF.

The IGA will be performed by the investigator at selected scheduled clinic visits.

SCORing Atopic Dermatitis (SCORAD) and Objective-SCORAD (O-SCORAD)

The validated SCORAD index uses the rule of nines to assess disease extent and evaluates six clinical characteristics to determine disease severity: (1) erythema, (2) edema/papulation, (3) oozing/crust, (4) excoriation, (5) lichenification, and (6) dryness (ETFAD 1993). The SCORAD index also assesses subjective symptoms of pruritus and sleep loss. These three domains (extent of disease, disease severity, and subjective symptoms) combine to give a maximum possible score of 103. The objective SCORAD consists of the extent and the intensity items, and the maximal possible O-SCORAD score is 83. Assessments will be recorded in the eCRF.

The SCORAD will be assessed at selected scheduled clinic visits.

The SCORAD and O-SCORAD will be computed at the dataset level, irrespective of its presence in the eCRF and the resulting calculated values will be utilized for the efficacy analysis. The SCORAD index will be calculated as specified in the [Appendix 12.4](#).

Itch and Sleep Quality Numerical Rating Scale (NRS)

At scheduled and unscheduled clinic visits, participants will assess the worst intensity itch due to AD per an NRS (WI-NRS, where 0 = "none" and 10 = "worst imaginable") [REDACTED]
[REDACTED].

At scheduled clinic visits, participants will assess sleep quality per an NRS (SQ-NRS, where 0 = "best possible sleep" and 10 = "worst possible sleep") [REDACTED]
[REDACTED].

4.5.2.2 Other Exploratory Endpoints

Other exploratory efficacy endpoints are:

- Change from baseline in percent body surface area (BSA) by visit
- Change from baseline in PGIS by visit
- Proportion (%) of participants with PGIS of 0 or 1 by visit
- Proportion (%) of participants reporting PGIC of “much better” or “a little better” by visit
- Change from baseline in DLQI by visit
- Proportion (%) of participants achieving \geq 4-point reduction from baseline in DLQI by visit in participants with DLQI \geq 4 at baseline

Body Surface Area (BSA)

The BSA assessment estimates the extent of disease or skin involvement with respect to AD and is expressed as a percentage of total body surface. BSA will be determined by the investigator using the rule of nines.

Participant will undergo this assessment at selected scheduled clinic visits.

Patient Global Impression of Severity (PGIS) of AD

At the scheduled clinical visits, participants will rate the severity of their AD over the past week on a 5-point scale ranging from 0 = “none” to 4 = “very severe”.

Patient Global Impression of Change (PGIC) of AD

At the scheduled clinical visits, participants will rate the change in their AD on a 5-point scale ranging from 1 = “much better” to 5 = “much worse”. Participants will be asked to provide this rating in comparison to just before the participant started taking study treatment.

Dermatology Life Quality Index (DLQI)

The DLQI is a validated 10-question instrument used to measure the impact of skin disease on the quality of life (QoL) of an affected person over the previous week. The ten questions cover the following topics: symptoms, embarrassment, shopping and home care, clothes, social and leisure, sport, work or study, close relationships, sex, and treatment (Finlay, Khan. 1992). The DLQI score ranges from 0 (no impact of skin disease on QoL) to 30 (maximum impact on QoL).

The DLQI is completed by the participant in the study clinic. Assessments will be recorded in the eCRF.

4.6 Safety Variables

4.6.1 Adverse Events and Serious Adverse Events Variables

Adverse events and serious adverse events will be collected from the time of informed consent signature until the end of the study. All adverse events will be coded according to the latest available version (26.0 or higher) of MedDRA.

An **Adverse Event** is the development of any untoward medical occurrence in a participant or clinical study participant who is administered with a medicinal product that does not necessarily have a causal relationship with this treatment. An AE can therefore be any unfavorable and unintended sign, symptom, or disease temporally associated with the use of a medicinal product, whether or not considered related to the medicinal product, including the following conditions:

- 1) Any newly occurred undesirable medical condition (including newly diagnosed disease or signs and symptoms when a diagnosis is pending);
- 2) Exacerbation of a chronic or intermittent pre-existing condition including either an increase in frequency and/or intensity of the condition. However, events that are unequivocally due to natural disease progression of the underlying disease being studied should not be reported as an AE during the study unless judged by the investigator to be more severe than expected for the participant condition;
- 3) Clinically significant laboratory abnormality.

A **Serious Adverse Event** is defined as any untoward medical occurrence that, at any dose, meets one or more of the criteria listed:

- **Results in death**
- **Is immediately life threatening**
- **Requires in-patient hospitalization or prolongation of existing hospitalization**
- **Results in persistent or significant disability or incapacity**
- **Is a congenital abnormality or birth defect**
- **Is an important medical event** (i.e., that may jeopardize the participant or may require medical treatment to prevent one of the outcomes listed above.)

Details for each criterion above are presented in the study protocol section 8.1.2.

Non-treatment emergent AEs (non-TEAEs) are AEs that are developed or worsened in severity compared to the baseline during the period between participant enrolment and study drug administration. all AEs collected during the screening period are considered as non-TEAEs.

Treatment-emergent AEs (TEAEs) are AEs that developed or worsened in severity compared to the baseline during the treatment and follow-up period. As only the worsening pre-existing AEs and new AEs reported during the treatment and follow-up period will be collected in the study, all AEs collected during the treatment and follow-up period are considered as TEAEs.

TEAE that are infusion related reaction will be summarized. These TEAEs are localized injection/infusion reactions that may include pruritus, pain, erythema, swelling, rashes, or bleeding around the injection/infusion site. Systemic injection/infusion-related reactions may be immediate type or delayed type immune complex-associated hypersensitivity reactions (e.g., serum sickness).

4.6.2 Laboratory Safety Variables

Hematology, chemistry, urinalysis, and pregnancy testing samples will be drawn at the timepoints as described in the Schedule of assessment (SoA) ([Appendix 12.1](#)) and analyzed at central laboratories.

Hematology	Serum chemistry ^a	Urinalysis ^b
Red blood cell count	Total protein	pH
Hemoglobin	Albumin	Glucose
Reticulocyte %	Alkaline phosphatase	Protein
White blood cell count	Total bilirubin	Blood
Neutrophils %	Aspartate aminotransferase	Ketones
Neutrophils	Alanine aminotransferase	Nitrite
Lymphocytes %	Lactate dehydrogenase	Leukocyte
Lymphocytes	Sodium	Urobilinogen
Monocytes %	Potassium	Bilirubin
Monocytes	Chloride	Specific gravity
Eosinophils %	Urea/ blood urea nitrogen	
Eosinophils	Creatinine	
Basophils %	Calcium	
Basophils	Phosphate	
Platelets	Uric acid	
	Glucose	
Other tests		
HBsAg		
HBsAb		
HBcAb		
HCV antibody		
HIV antibody		
QuantiFERON-TB Gold or an equivalent test		
Pregnancy test (women of childbearing potential only) ^c		
Serum tryptase ^d		

- a) Fasting is recommended but not mandatory. The status of fasting or non-fasting should be recorded in the study source document.
- b) If any abnormalities are found in urinalysis, then microscopy should be conducted to examine red cells, white cells, bacteria, casts, and crystals.
- c) Serum human chorionic gonadotropin (hCG) will be performed at the Screening, Baseline (Day 1), Week 2 (Day 15), Week 4 (Day 29) visits, and at selected follow-up visits. In addition, urine pregnancy test must be performed prior to dosing at Baseline (Day 1), Week 2 (Day 15) and Week 4 (Day 29).
- d) For diagnostic purposes, any participant who experiences any systemic infusion-related event should have a blood sample taken ideally 30-60 minutes after the onset for tryptase testing, and samples may be analyzed by a central or local laboratory.

4.6.3 Vital Signs and Physical Examination Variables

The following vital signs (VS) parameters will be collected:

- Weight (kg) and height (cm)
- Systolic and diastolic blood pressure (mmHg)
- Pulse rate (bpm)
- Temperature (C)
- Respiratory rate (breaths/min)

Weight and height will be measured only at baseline. Other vital signs parameters will be collected as specified in the SoA ([Appendix 12.1](#)). On study treatment dosing days, i.e., Baseline (Day 1), Week 2 (Day 15), and Week 4 (Day 29), vital signs should be assessed before initiation of infusion; 15 (\pm 5) minutes after the initiation of the infusion; 15 (\pm 5) minutes after end of infusion (EOI), and 1 hour (\pm 15 minutes) post EOI.

A complete physical examination will include, at a minimum, assessments of the skin, head and neck, cardiovascular, respiratory, gastrointestinal, and neurological systems and the assessment will be performed as specified in the SoA ([Appendix 12.1](#)).

A brief physical examination will include, at a minimum, assessments of the skin, lungs, cardiovascular system, and abdomen (liver and spleen). Symptom-directed physical examinations will be completed at each follow-up visit at the discretion of the investigator.

Investigators will be instructed to pay special attention to clinical signs related to previous serious illnesses. Unscheduled physical examinations can be conducted at the discretion of the PI or designee.

4.6.4 12-Lead Electrocardiogram (ECG) Variables

The following ECG parameters will be collected along with their corresponding clinical significance:

- Heart rate (bpm)
- PR interval (msec)
- QRS interval (msec)
- QT interval (msec)
- QTcB interval (msec)
- QTcF interval (msec)

Triplet ECG will be taken if there are any clinically significant abnormalities detected by the physician in a single ECG. The ECG assessment will be performed at timepoints listed in the SoA ([Appendix 12.1](#)).

4.7 Pharmacokinetic (PK) Variables

The blood samples will be collected at day 1/baseline (pre-dose and EOI), days 8, 15 (pre-dose and EOI), 29 (pre-dose and EOI), 43, 57, 85/EOT, 113, 141, and 169/EOS to describe IMG-007 concentration profiles at specified visit.

4.8 Immunogenicity Variable

The variables include anti-drug antibody (ADA) status (positive or negative) as follows:

- Total participants negative in the ADA assay at all time points analyzed
- Total participants positive in the ADA assay at any time point analyzed
- Total participants with pre-existing ADA
- Total participants with treatment emergent response
- Total participants with treatment boosted response
 - *Pre-existing ADA*: Either an ADA positive response in the assay at baseline with all post first dose ADA results negative, OR a positive response at baseline with all post first dose ADA responses less than 4-fold over baseline titer levels.
 - *Treatment-boosted response*: Pre-existing ADA that is increased to a higher concentration (4-fold or higher level) after administration of therapeutic protein product.
 - *Treatment-emergent response*: ADA developed de novo (seroconversion) following administration of therapeutic protein product in a participant who lacked detectable pre-existing ADA
 - a. *Persistent response*: Treatment-emergent response detected at 2 or more sampling time points during the treatment (including follow-up period if any), where the first and last ADA-positive samples (irrespective of any negative samples in between) are separated by a period of 16 weeks or longer.
 - b. *Indeterminate response*: as a treatment-emergent response with only the last collected sample positive in the ADA assay
 - c. *Transient response*: Treatment-emergent response detected only at 1 sampling time point during the treatment or follow-up observation period, or 2 or more time points during the treatment, where the first and last ADA-positive samples are separated by a period less than 16 weeks, and the participant's last sampling timepoint is ADA-negative.

Blood sample for the immunogenicity analysis will be collected at Day 1/Baseline (pre-dose), days 15(pre-dose), 29 (pre-dose), 43, 57, 85/EOT, 113, 141, and 169/EOS.

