7.4 Pharmacokinetics and Immunogenicity Assessments

Blood will be collected to describe the IMG-007 PK and immunogenicity profiles as outlined in [Table 5](#).

Participants with signs of any potential immune response to IMG-007 will be closely monitored with clinical evaluations. The PK and ADA samples may be collected at unscheduled visits for further evaluation.

Details concerning handling of PK and ADA serum samples, including labeling and shipping instructions, will be provided in the Laboratory Manual. The actual time each sample was collected will be captured to the nearest minute in the eCRF and recorded in the database.

Samples will be shipped to the laboratory where samples will be analyzed for serum IMG-007 concentrations using a validated method.

Validated screening and confirmatory assays will be employed to detect ADAs at multiple timepoints throughout the study.

The immunogenicity evaluation will utilize a risk-based immunogenicity strategy ([Bai et al. 2012](#); [Rosenberg et al. 2004](#)) to characterize ADA responses to IMG-007 in support of the clinical development program.

Table 5 PK and ADA Sampling Schema

Dose No.	Day	Pre-dose /Post-dose	PK blood sampling time	ADA sampling time	Sampling Window
1	1	Pre-dose	0 (pre-dose)	0 (pre-dose)	- 2 hours
	1	Post-dose	EOI	--	+10 mins
	8	Post-dose	7 days post-dose	--	± 3 days
2	15	Pre-dose	0 (pre-dose)	0 (pre-dose)	- 2 hours
	15	Post-dose	EOI	--	+10 mins
3	29	Pre-dose	0 (pre-dose)	0 (pre-dose)	- 2 hours
	29	Post-dose	EOI	--	+10 mins
	43	Post-dose	14 days post-dose	14 days post-dose	± 3 days
57	Post-dose	28 days post-dose	28 days post-dose	± 3 days	
	85/EOT	56 days post-dose	56 days post-dose	± 3 days	
113	Post-dose	84 days post-dose	84 days post-dose	± 3 days	
141	Post-dose	112 days post-dose	112 days post-dose	± 3 days	
169/EOS	Post-dose	140 days post-dose	140 days post-dose	± 3 days	

Abbreviations: ADA = anti-drug antibody; EOI = end of Infusion; EOT = end of treatment; EOS = end of study; PK = pharmacokinetic

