6.12 Analysis of Immunogenicity Data

The ADA variables will be summarized using descriptive statistics in the immunogenicity analysis set. Frequency tables of the proportion of participants developing ADA positivity in the ADA assay, pre-existing ADA, treatment-emergent, treatment-boosted, persistent, indeterminate and transient ADA responses will be presented as absolute occurrence (n) and percent of participants (%).

Listing of ADA data will be provided.

The following summaries will be performed on the immunogenicity analysis set:

- Number (%) of patients negative ADA at all the time points analyzed
- Number (%) of patients ADA positive at time points analyzed
- Number (%) of patients with pre-existing ADA, treatment-emergent ADA, and treatment boosted ADA response
- Number (%) of patients with persistent, transient and indeterminate treatment-emergent ADA response
- Descriptive statistics of PK concentration in ADA positive and ADA negative participants.

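### SAP 4.8 defines treatment-boosted ADA through a pre-existing ADA definition that already rules out a 4-fold rise, so read literally the boosted category in the SAP 6.12 table is empty

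*SAP*

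**What the plan says.** SAP 4.8 gives pre-existing ADA two alternative limbs. The first is "Either an ADA positive response in the assay at baseline with all post first dose ADA results negative". The second is "a positive response at baseline with all post first dose ADA responses less than 4-fold over baseline titer levels". The next definition, treatment-boosted response, is "Pre-existing ADA that is increased to a higher concentration (4-fold or higher level) after administration of therapeutic protein product". The third, treatment-emergent response, is "ADA developed de novo (seroconversion) following administration of therapeutic protein product in a participant who lacked detectable pre-existing ADA".

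The same section also lists "Total participants positive in the ADA assay at any time point analyzed", which does not depend on any of the three definitions.

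SAP 6.12 then calls for "Number (%) of patients with pre-existing ADA, treatment-emergent ADA, and treatment boosted ADA response" and redefines none of the terms. It also plans PK concentrations by ADA-positive and ADA-negative status and a listing of ADA data. Protocol 11.3.4 and SAP section 5 contain no ADA category definitions. No redaction is visible in any of these sections.

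On the assay side, Protocol 7.4 says "Validated screening and confirmatory assays will be employed to detect ADAs at multiple timepoints throughout the study". Neither document names the source of the titre used for the 4-fold comparison.

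**The concern.** The boosted category exists to show one thing: a participant who already had antibody before dosing and whose antibody rose afterwards. The definition uses a term that, one item earlier, was limited to people in whom this did not happen. A programmer who applies the SAP's own defined term gets a row that cannot be filled, and a participant with the signal of interest has no row in the three-way split. A programmer who works from the presumed intent gets a different table. Both can claim to have followed the SAP.

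A second ambiguity sits on top. One definition speaks of titre and the other of concentration, and the source of the measurement is not stated. A printed count of zero boosted could then mean that nobody was boosted, that the definition was empty, or that titres were not available. The table would not show which.

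At stake is the reading of one immunogenicity table. Immunogenicity is an exploratory objective (Protocol Table 3), and Protocol 2.6 and 6.6 list it among the potential safety risks.

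**Working it through.** The plan states no figure on this point, so there is none to reproduce. The check is one of logic, followed by a count.

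**Inputs**
- Definitions: SAP 4.8, as quoted above.
- Post-baseline ADA samples: 8, on Days 15, 29, 43, 57, 85, 113, 141 and 169 (SAP 4.8).
- Participants enrolled: 13 (Protocol 4.1).
- Baseline ADA prevalence: not given. A range of 1% to 20% is assumed, for illustration only.

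**Step 1: set the conditions side by side for a baseline-positive participant**
- Pre-existing: every post-dose result is negative, or every post-dose response is below 4-fold.
- Boosted: pre-existing, and at least one post-dose response is 4-fold or more.
- No response below 4-fold is also 4-fold or more, so the two conditions for boosted cannot both hold.
- Treatment-emergent cannot take the participant either, because someone positive at baseline has not seroconverted de novo.

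**Step 2: enumerate**

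Let each of the 8 samples be negative, positive below 4-fold, or positive at 4-fold or more. There are 3^8 = 6,561 patterns. Those with no result at 4-fold or more number 2^8 = 256, which leaves 6,561 − 256 = 6,305.

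| Category (baseline-positive participant) | SAP 4.8 read literally | Split proposed under the fix |
|---|---|---|
| Pre-existing (not boosted) | 256 | 256 |
| Treatment-boosted | 0 | 6,305 |
| Treatment-emergent | 0 | 0 |
| None of the three | 6,305 | 0 |
| More than one | 0 | 0 |

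These are counts of patterns, not probabilities. They show only that the literal definitions leave a gap and that the proposed split is exhaustive and exclusive when titres are available.

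**Step 3: what remains visible**

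The immunogenicity set requires an evaluable baseline result (SAP 3.4). Anyone ever positive is therefore either baseline-positive or treatment-emergent, which gives

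baseline-positive = positive at any time point − treatment-emergent.

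This holds even on the literal reading. Subtracting the pre-existing count then leaves the unclassified participants. If titres are missing, that remainder also mixes in participants who could not be assessed.

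**Step 4: size**

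One participant is 1/13 = 7.7 percentage points if all 13 are in the immunogenicity set. The chance of at least one baseline-positive participant among 13 is 1 − (1 − q)^13 for prevalence q:
- q = 1%: 12%
- q = 5%: 49%
- q = 10%: 75%
- q = 20%: 95%

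For a given q these are upper bounds on how often the definition matters, because the participant must also have a 4-fold rise.

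**The case against.** The best defence is that the contradiction needs one particular reading. The treatment-emergent definition uses pre-existing ADA in its ordinary sense, antibody present before dosing. Read that way in the boosted definition too, the two categories share one 4-fold cut and divide the baseline-positive participants cleanly. SAP 6.12 gives boosted its own output, so its authors plainly expected that it could be filled. This stands as an account of intent and keeps the point small. It does not repair the text, because the ordinary and the defined sense appear in the same list and nothing says which one governs.

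Four stronger conclusions are tempting, and the documents do not support them.
- *That boosted will be reported as zero whatever the data show.* This assumes that the literal rule is programmed. The intended rule is easy to infer and may well be used instead.
- *That participants disappear, or that the number positive at baseline cannot be found.* They stay in the any-time positive count, the ADA-positive PK summary and the listing. On the intended reading, pre-existing plus boosted is the baseline-positive count. On the literal reading, step 3 of the working recovers it.
- *That treatment-related ADA incidence, emergent plus boosted, is understated.* The SAP names no such output. Only someone who formed that sum from a literally programmed table would be misled.
- *That titres were not measured.* Protocol 7.4 mentions only detection assays, but SAP 4.8 itself refers to baseline titre levels, and neither document says that samples are not titrated. Silence supports asking for the source and nothing more.

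**Conclusion.** The definition is wrong as written and should be corrected, but its reach is narrow. Read literally, the boosted category is empty, and a baseline-positive participant with a rise of 4-fold or more has no place in the three-way split. The effect stops at a descriptive exploratory table; the primary endpoint (treatment-emergent adverse events) and the secondary endpoint (percentage change in EASI at Week 12) are untouched.

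The 7.7-point figure rests on two assumptions: that all 13 enrolled participants meet the immunogenicity set criteria, and that a participant of this kind exists. The documents give neither the size of that set nor any baseline ADA result, so the number affected is unknown and may be zero.

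**What to change.** Replace the two definitions in SAP 4.8 with one parent category and its parts, and carry the same labels into SAP 6.12:

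- *Baseline-positive ADA*: positive at baseline, whatever follows.
- *Treatment-boosted*: baseline-positive, with any post-dose titre at least 4-fold the baseline titre.
- *Pre-existing, not boosted*: the remaining baseline-positive participants.
- *Not evaluable for boosting*: baseline-positive participants without the titres needed to decide. They are shown in their own row and not counted as not boosted. A participant whose post-dose samples are all negative needs no titre and is not boosted.

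Use titre in both definitions and name the assay or data transfer that supplies it. Print the baseline-positive total above its parts so that the rows can be seen to add up.

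The cost is a few lines of SAP text and one table shell. No new data are needed. If titres turn out not to be available, the affected participants are reported as not evaluable.
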